Following an initial dose at 45-80 mg/m², all subjects tested on ADVL0812 showed peak plasma concentrations of MLN8237 well in excess of 1 μ M, with peak concentrations in the range of 2-10 μ M. MLN8237 was rapidly absorbed after an oral dose, with a median (range) T_{max} of 2.3 (1.1-3.1) hours. At the recommended single-agent phase 2 dose (80 mg/m² PO once daily) the mean AUC_{0-24} was 75.2 μ M•h. Wide interpatient variability in drug disposition was observed. The median (range) half-life was 7.34 (6.13-8.64) hours. The median (range) apparent clearance (CL/F) was 34 (16-59) ml/min/m², and CL/F was similar in males (36 ml/min/m²) and females (32 ml/min/m²). These preliminary pediatric pharmacokinetic results suggest that drug concentrations used in preclinical studies are clinically attainable at the dosing range proposed in this study.

Table 2. Details of dose escalation on phase I portion of COG protocol ADVL0812.

Dose Level	Number of Evaluable Patients	Number of Courses	Number of Patients with Cycle 1 DLT
45 mg/m ² /dose once daily	6	6	1
60 mg/m ² /dose once daily	5	28	0
80 mg/m ² /dose once daily	6	21	1
100 mg/m ² /dose once daily	4	9	3
80 mg/m ² /day BID	6	9	2
60 mg/m ² /day BID	5	17	1

MLN8237 was initially formulated as a capsule. Considerable inter-patient variability in the pharmacokinetic profile of this agent was observed, and was thought to be at least partially attributable to its formulation. For this reason an enteric-coated tablet has been developed. This formulation results in more consistent pharmacokinetic results. In adults (n=22) the relative bioavailability of the enteric coated tablet formulation in reference to the original powder in capsule formulation was 90% (90% CI, 74.4, 108.8).{Dees, 2012 #34} In addition, the enteric coated tablet formulation has already been shown to be well-tolerated in adults using doses of up to 40 mg by mouth twice daily, which is 80% of the adult MTD with the previous capsule formulation. This study will utilize the enteric-coated tablet formulation for patients who are able to swallow intact pills.

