2.12 Rationale for Amendment #5

Amendment #4 was an administrative amendment.

Amendment #5 designates the recommended phase 2 dose for this regimen when used with enteric coated tablets. After Amendment #3, dose levels 1B, 2B, and 3B were evaluated in the phase 1 portion of the study. At dose level 1B, 0 / 6 patients had first-course DLT. At dose level 2B, 1 / 6 patients had first-course DLT (prolonged grade 4 neutropenia). At dose level 3B, 2 / 4 evaluable patients had first-course DLT (prolonged grade 4 neutropenia; failure to meet platelet criteria by Day 35 of course 1). This experience established the recommended phase 2 dose as dose level 2B when used with MLN8237 enteric coated tablets. With Amendment 5, the phase 2 portion of the study is open to patients who are able to swallow intact pills. Patients on the phase 2 portion will begin therapy at dose level 2B and will utilize the enteric coated tablet formulation.

Amendment #5 also adds a cohort of patients treated with an MLN8237 oral solution. This new solution will provide access to patients who are unable to swallow intact pills. The pharmacokinetics of an oral solution formulation of MLN8237 was evaluated in 17 adult patients who participated in a cross-over relative bioavailability study evaluating both the powder-in-capsule formulation (with similar bioavailability to the current enteric coated tablet formulation) and the oral solution. The geometric mean ratios (oral solution in reference to the powder-in-capsule) for exposure (AUC_{inf}) and peak plasma concentration (C_{max}) were determined as 1.26 (90% CI 1.09-1.47) and 1.90 (1.52-2.37), respectively (Investigator Brochure). Based upon these results, pediatric patients receiving single-agent MLN8237 as the oral solution are recommended to receive $60 \text{ mg/m}^2/\text{dose}$ instead of the standard pediatric dose of 80 mg/m^2 obtained with intact pills. In the context of the current combination regimen in which the recommended phase 2 MLN8237 dose with enteric coated tablets is $60 \text{ mg/m}^2/\text{dose}$, patients in the oral solution cohort will begin therapy at dose level 1B with 45 mg/m^2 MLN8237. Patients in this cohort will exclusively receive the oral solution and will be required to participate in pharmacokinetic testing.

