10.0 STATISTICAL CONSIDERATIONS

10.1 Sample Size and Study Duration

Design of the Completed Phase I Portion: Two to six evaluable patients will be entered at each dose level for determination of the maximum tolerated dose. The minimum sample size required to identify the MTD is 15 patients. The maximum sample size for the phase 1 portion, assuming all 4-dose levels plus the initial dose level 1 require 6 patients before the MTD is determined, is 30 patients. This estimate assumes that all patients are fully evaluable. Review of the enrollment rate onto recent non-MIBG NANT studies indicates that 1-2 patients per month are available for the phase I portion of the study. For example, NANT protocols N01-03 (CEP-701), N03-01 (oral irinotecan and temozolomide), and N04-04 (oral fenretinide) have each enrolled approximately 8 patients per year, not accounting for closure time due to protocol amendments and drug supply issues. These patient numbers predicted identification of the MTD within approximately 12-18 months. *(The phase 1 portion required 22 patients and 18 months to complete.)*

Phase 2 Portion: The phase 2 portion of the study will enroll 14-20 new patients based on the two-stage design. Review of enrollment to date to the phase 2 portion indicates that 2 patients with neuroblastoma per month are available for this portion of the study. We anticipate that the phase 2 portion of the study will be completed within 12 months.

The oral solution cohort will enroll 6-18 patients, though only patients unable to swallow pills will enroll to this cohort. We expect 1 patient per month will be available, allowing completion of this cohort in 6-18 months.

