10.5 Statistical Rules for Oral Solution Cohort

Up to 6 patients evaluable for dose escalation consideration (section 10.2.1) will be enrolled at the starting dose level for this cohort (dose level 1B = one dose level below the phase 2 dose obtained with enteric coated tablets), following the rolling-six rules in section 10.3. After enrollment to this dose level is complete, the toxicity and pharmacokinetic parameters will be assessed by the study committee.

If dose de-escalation is indicated based upon toxicity at dose level 1B, this will occur following the rolling-six rules in section 10.3 and will occur independent of pharmacokinetic results.

If dose escalation appears feasible based upon toxicity at dose level 1B, this will occur following the rolling-six rules in section 10.3 only if the study committee determines that MLN8237 exposures are below predicted levels at dose level 1B. This provision is in place since dose level 2B with the oral solution is predicted to be comparable to dose level 3B with the tablet formulation and that dose level was not tolerable in the phase 1 portion of the study.

Once the MTD with the oral solution has been determined, the study committee will assess the pharmacokinetic parameters to determine if enrollment of up to additional 6 patients at the MTD will be needed to better characterize the pharmacokinetic profile of the oral solution. Interpatient variability and comparison with exposures obtained with oral solution and enteric coated tablets will be used to drive this determination.

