10.8 Pharmacokinetic and Correlative Biology Studies

Routine pharmacokinetic parameters for both MLN8237 and irinotecan will be determined using standard methods and reported descriptively. After completion of the phase II portion of the study, a final pharmacokinetic analysis will be performed that incorporates results from the phase I, phase II, and oral solution cohort portions of the study. Parameters to be determined include exposure, clearance, C_{max} , T_{max} , C_{ss} , and terminal half-life for both MLN8237 and irinotecan. These parameters will be assessed for both the enteric coated tablet formulation and for the oral solution formulation. These parameters will be qualitatively compared with estimates from prior studies of MLN8237 and irinotecan as single agents. In addition, these parameters for MLN8237 will be qualitatively compared between the enteric coated tablet and oral solution formulations.

The correlative biology studies are considered descriptive. For the study of *UGT1A1* genotype and toxicity, patients will first be categorized according to the number of *UGT1A1*28* alleles (0, 1, or 2 copies of the allele). Association between *UGT1A1* genotype and occurrence of (any) DLT and diarrhea will then be examined qualitatively. For the study of Aurora A expression, patients will first be categorized as having “high” or “low” Aurora A tumor expression for both mRNA and protein (using a median split). Association between Aurora A expression, response and EFS will then be examined. Similarly, associations between *MYCN* amplification status and Aurora A expression (mRNA and protein), response and EFS, and will be examined. These descriptive analyses will use contingency tables, scatterplots, and Kaplan-Meier plots, as well as corresponding quantitative measures of association. Association between *AURKA* genotype and objective response will be examined qualitatively. Patients will be categorized according to genotype at the two *AURKA* SNPs of interest (homozygous wild type; heterozygous; homozygous minor allele), with the percent of patients with at least a partial response or better given in each category.

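### Section 10.8 compares tablet and oral-solution pharmacokinetics only qualitatively, so primary Aim 1.3 would end with no ratio or interval for the formulation difference

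*Combined protocol and SAP*

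**What the plan says.** Aim 1.3 (Section 1.0) is a primary aim and covers irinotecan and both MLN8237 formulations. Section 10.8 lists exposure, clearance, Cmax, Tmax, Css and terminal half-life, pools phase 1, phase 2 and oral-solution data in a final analysis, and then states that "these parameters for MLN8237 will be qualitatively compared between the enteric coated tablet and oral solution formulations".

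Section 10.5 uses exposure data twice. Escalation of the solution from level 1B to 2B, if toxicity allows, occurs "only if the study committee determines that MLN8237 exposures are below predicted levels at dose level 1B". The reason given is that "dose level 2B with the oral solution is predicted to be comparable to dose level 3B with the tablet formulation", a tablet level that was not tolerable. Later, the committee compares solution with tablet exposures to decide whether "enrollment of up to additional 6 patients at the MTD will be needed to better characterize the pharmacokinetic profile".

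On numbers, "The oral solution cohort will enroll 6-18 patients" (Section 10.1), with up to 6 evaluable at the starting level (Section 10.5). On variability, Section 2.6 reports for the earlier capsule: "Wide interpatient variability in drug disposition was observed".

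**The concern.** A qualitative comparison of two small groups gives the reader two sets of summary statistics and an impression. It does not say how large the formulation difference is or how well it is known, and later dosing of the solution would depend on both. The comparison also has a use inside the trial, because it helps decide whether to enrol up to 6 more patients for pharmacokinetics.

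The groups also differ in dose. If AUC and Cmax are tabulated without normalisation, solution at 45 mg/m² set beside phase 2 tablets at 60 mg/m² mixes the dose difference with the formulation difference. On the documents' own adult ratios, the two nearly cancel for AUC.

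**Working it through.** **Inputs from the documents.**
- Solution/capsule ratios, 17 adults: "were determined as 1.26 (90% CI 1.09-1.47) and 1.90 (1.52-2.37), respectively" for AUC and Cmax (Section 2.12).
- Tablet/capsule relative bioavailability, 22 adults: 0.90 (90% CI 0.744–1.088) (Section 2.6).
- CL/F in children on the capsule: median 34, range 16–59 ml/min/m² (Section 2.6).
- Phase 1 tablet patients: 6 at level 1 (Section 2.11), then 6 at 1B, 6 at 2B and 4 evaluable at 3B (Section 2.12). The sum, 22, matches the count in Section 10.1. Section 6.1 gives the formulation as the tablet, and Section 8.0 made sampling mandatory for these patients.

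**Checking the plan's cohort size.** One level of 6 gives 6. Level 1B, one further level and the expansion give 6 + 6 + 6 = 18. This reproduces 6–18.

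**What the adult ratios predict for AUC.**
- Per mg, solution/tablet: 1.26 / 0.90 = 1.40. On the log scale the two 90% half-widths are ln(1.47/1.09)/2 = 0.150 and ln(1.088/0.744)/2 = 0.190. Treated as independent they combine to 0.242, so the ratio is roughly 1.10 to 1.78.
- Not normalised, solution 45 against tablet 60: (45 × 1.26) / (60 × 0.90) = 56.7 / 54.0 = 1.05.
- Not normalised, solution 45 against tablet 45: 1.40. Levels 1 and 1B give up to 6 + 6 = 12 tablet patients for this comparison.

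**Between-patient spread (assumption).** No SD is stated. ln(59/16) = 1.305. The expected range of 15 to 37 normal values is about 3.5 to 4.3 SDs, so log-SD is about 0.31 to 0.38. The number of patients behind the range is not given, so 15 to 37 is assumed. I use 0.35, with 0.30–0.50 as the range.

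**Precision of a solution/tablet geometric mean ratio.** The 90% CI is the estimate multiplied and divided by exp(t × SD × √(1/n_tablet + 1/n_solution)), with t the 95th percentile on n_tablet + n_solution − 2 degrees of freedom.

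| Tablet | Solution | t | √ term | SD 0.30 | SD 0.35 | SD 0.50 |
|---|---|---|---|---|---|---|
| 22 | 6 | 1.706 | 0.461 | 1.27 | 1.32 | 1.48 |
| 22 | 18 | 1.686 | 0.318 | 1.17 | 1.21 | 1.31 |
| 12 (45 mg/m² only) | 6 | 1.746 | 0.500 | 1.30 | 1.36 | 1.55 |

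Optional phase 2 samples would add tablet patients.

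**What "only if the study committee determines that MLN8237 exposures are below predicted levels at dose level 1B" leaves open.** In capsule-equivalent terms, 45 mg/m² of solution is 45 × 1.26 = 56.7 mg/m² on AUC (49 to 66 across the CI) but 45 × 1.90 = 85.5 mg/m² on Cmax. The prediction therefore depends on a parameter that Section 10.5 does not name.

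**Two sections side by side.** Section 4.3 ties both escalation to 2B and de-escalation to −1B to pharmacokinetic data at 1B. Section 10.5 makes toxicity-driven de-escalation independent of pharmacokinetic results.

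**The case against.** The strongest reply is that the plan already contains a normalised comparison. Oral clearance is dose divided by AUC, so a 1.40-fold AUC difference per mg would appear as a 1.40-fold CL/F difference. That stands, and it would be wrong to say the comparison is not dose-normalised. What remains is that no ratio or interval is planned for CL/F, and Cmax has no normalised counterpart.

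It can also be said that tablet data exist at the solution's starting dose. That stands too. The near-cancellation to 1.05 applies only against 60 mg/m² patients, so the planned data do not hide the formulation effect.

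Third, Aim 1.3 is to characterise, the cohort's primary endpoint is toxicity, and patients are allocated by ability to swallow pills (Section 3.2.6). A between-group ratio therefore mixes formulation with patient characteristics. This is a reason to label the ratio descriptive, not to omit it.

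A reader might infer from Section 10.5 that the pharmacokinetic condition is met half the time when exposure is exactly as predicted. The documents do not support that as a property of the plan. Half is what follows if a bare point estimate is compared with its own true value, at any sample size. Section 10.5 sets no such rule: it sets a committee judgement, added to the rolling-six toxicity rules, and level 2B would have its own rolling-six stop.

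**Conclusion.** The point holds for Section 10.8. The comparison of formulations under a primary aim has no planned estimate or interval, and normalisation of AUC and Cmax is unspecified. With 22 tablet patients, the ratio could be reported to within a factor of about 1.32 (6 solution patients) or 1.21 (18) at an assumed log-SD of 0.35. Over 0.30–0.50 the factors are 1.27–1.48 and 1.17–1.31. Against an anticipated AUC ratio near 1.40, that is informative though not tight.

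These figures assume log-normal exposure, equal spread in both groups, and a spread inferred from capsule data, which Section 2.6 thinks more variable than the tablet. Pooling across dose levels also relies on the approximate dose-proportionality reported in Section 2.6.

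For Section 10.5 the conclusion is narrower: the parameter and predicted value are not stated, AUC and Cmax imply different predictions, and the text on de-escalation conflicts with Section 4.3. It does not follow that the escalation condition is unsafe. A confidence-limit rule is not clearly better either: with 6 patients, a one-sided 90% limit would be met only 39–56% of the time (log-SD 0.50–0.35) when exposure is truly 20% low.

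**What to change.** 1. In Section 10.8, replace the qualitative comparison of formulations with solution/tablet geometric mean ratios and 90% CIs, on the log scale, for dose-normalised AUC0-24 (equivalently CL/F) and dose-normalised Cmax. Use all phase 1, phase 2 and oral-solution data. Normalise by the dose actually given per m², because tablets are rounded to 10 mg: in Appendix II, 20 mg at the 45 mg/m² level is 20/0.38 = 52.6 mg/m² at one end of its band and 20/0.55 = 36.4 at the other.
2. Add a sensitivity comparison restricted to 45 mg/m² (up to 12 phase 1 tablet patients), which does not rely on dose-proportionality.
3. State that the ratios are descriptive and non-randomised.
4. In Section 10.5, name the parameter and the predicted value. Showing the committee the 90% interval around the 1B geometric mean would inform its judgement: with 6 patients it spans a factor exp(2.015 × SD/√6), or 1.33 at SD 0.35 (1.28–1.51 over 0.30–0.50). No threshold is proposed.
5. Reconcile Sections 4.3 and 10.5 on the role of pharmacokinetic data in de-escalation.

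The cost is wording and a few lines of analysis on samples already planned, with no extra patients or blood draws.

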10.6 Analysis of Results

The outcome status (in terms of number of courses received, toxicity, response, reason off treatment, progression, and survival) of all registered patients will be reported.

10.6.1 Toxicity

All toxicities observed will be summarized in terms of type (organ affected or laboratory determination), severity (by NCI CTCAE), and attribution. Tables will be created to summarize these toxicities and side effects by tablet vs. oral solution, by dose level and by course. Particular emphasis will be placed on descriptions of diarrhea, mucositis, and myelosuppression.

10.6.2 Response/Outcome

All eligible patients who begin treatment will be included in the analysis of overall survival, event-free survival (EFS), and best response (defined in Section 11.0 below). Patients with measurable

or evaluable tumor who receive study therapy or who progress prior to completion of therapy will be included in a planned subset analysis of tumor response (per Section 5.2.2).

Overall survival is defined as the time from start of treatment until death due to any cause or time of last follow-up if the patient is alive at the last known follow-up. Event-free survival is defined as time from start of treatment to disease progression, development of a second malignancy, or death – whichever comes first; patients who are alive, have not progressed or developed a new malignancy will be censored at their last follow-up.

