The Aurora A kinase has been shown to play an important role in neuroblastoma growth. Inhibition of Aurora A kinase activity attenuates the growth of neuroblastoma cells. MLN8237 is a selective small molecule inhibitor of Aurora A kinase that has completed pediatric single-agent phase I testing, as well as stage 1 phase 2 testing in patients with Neuroblastoma. MLN8237 showed activity against the NCI-sponsored Pediatric Preclinical Testing Program neuroblastoma *in vivo* panel that exceeded the activity level observed with chemotherapy agents routinely used in the treatment of neuroblastoma. Additional *in vitro* and *in vivo* studies have shown that Aurora A kinase inhibitors result in enhanced cytotoxicity when used in combination with chemotherapy. Irinotecan and temozolomide is a commonly used salvage regimen for patients with relapsed or refractory neuroblastoma. This combination has a modest objective response rate (16%) and is well-tolerated, suggesting that it will provide a useful platform for the study of novel compounds in combination with chemotherapy. Preclinical studies demonstrate marked enhancement of anti-neuroblastoma activity with the addition of MLN8237 to irinotecan and temozolomide. This study therefore evaluates the tolerability and activity of MLN8237 in combination with irinotecan and temozolomide in children with refractory or relapsed neuroblastoma. Patients receive irinotecan (50 mg/m²/dose IV) and temozolomide (100 mg/m²/dose orally) once daily for 5 days along with MLN8237 orally once daily for 7 days. The doses of irinotecan and temozolomide will be fixed and the dose of MLN8237 will be dose-escalated. In the phase I portion of the study, the primary aims are to determine the recommended phase II doses of this combination, describe the toxicity of this combination, and characterize the pharmacokinetic profile of MLN8237 and irinotecan when used in combination. In the phase II portion of the study, the primary aim is to determine the objective response rate of this combination in patients with relapsed or refractory neuroblastoma. With Amendment 5, the tolerability and pharmacokinetics of an MLN8237 oral solution will be evaluated. Optional correlative studies will evaluate *UGT1A1* polymorphisms as predictors of toxicity and archival tumor tissue Aurora A expression as a predictor of response with this combination.

[figure not shown]
Hypothesis:

We hypothesize that:

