1.0 GOALS AND OBJECTIVES (SCIENTIFIC AIMS)

Primary Aims:

- 1.1 To estimate the maximum tolerated dose (MTD) of MLN8237 when given together with fixed doses of irinotecan and temozolomide in children and young adults with relapsed or refractory neuroblastoma.
- 1.2 To describe the toxicities of the combination of MLN8237, irinotecan, and temozolomide in children and young adults with relapsed or refractory neuroblastoma
- 1.3 To characterize the pharmacokinetics of irinotecan as well as MLN8237 enteric coated tablet and oral solution formulations in patients treated with this regimen
- 1.4 To determine the response rate for patients with relapsed or refractory neuroblastoma treated with MLN8237, irinotecan, and temozolomide at the identified MTD

Secondary Aim:

- 1.5 To determine the progression free survival rates for patients with relapsed or refractory neuroblastoma treated with MLN8237, irinotecan, and temozolomide at the identified MTD

Additional/Correlative Aims

- 1.6 To explore whether *MYCN* status and markers of expression of Aurora A in archival tumor tissue are associated with the antitumor activity of the combination of MLN8237, irinotecan, and temozolomide
- 1.7 To explore whether *UGT1A1* genotype is associated with toxicity in children with refractory neuroblastoma treated with the combination of MLN8237, irinotecan, and temozolomide
- 1.8 To explore whether *AURKA* genotype is associated with antitumor activity in children with refractory neuroblastoma treated with the combination of MLN8237, irinotecan, and temozolomide.

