2.13 Rationale for Amendment #6

Experience with this regimen prior to Amendment #6 has demonstrated that hematologic toxicity is the primary dose-limiting toxicity (DLT). However, some DLTs have been uncomplicated grade 4 neutropenia for > 1 week (to date, one episode in course 1 in the phase II portion in the absence of other DLT) or uncomplicated thrombocytopenia requiring platelet transfusions more than twice in a 1 week period (to date, one episode in course 1 in the phase II portion in the absence of other DLT). Having grade 4 neutropenia for > 1 week or need for multiple platelet transfusions during a nadir is consistent with the degree of hematologic toxicity seen in other common regimens used for patients with newly diagnosed high-risk neuroblastoma and in some regimens used in patients with relapsed disease. Therefore, with Amendment #6, these elements of the definition of hematologic DLT are removed. Hematologic DLT will be defined solely on the basis of delays in starting subsequent courses beyond day 36 due to failure to recover counts. Day 36 has been updated from Day 35, as that would be a true two week delay, and allowing for patients to stay on a Monday start schedule.

Prior to Amendment #6, the statistical design allowed up to 6 patients from the phase I portion of the trial to contribute to the phase II portion of the trial. Given early evidence of activity of this regimen, there is a desire to complete a full independent phase II evaluation of this regimen. Amendment #6 formally separates the phase I and phase II portions of the study and will require an additional 6 patients evaluable for response. Patient accrual to the phase II portion has been rapid, such that enrolling an additional 6 patients is feasible.

Amendment #6 also updates eligibility and response criteria for uniformity with other current active NANT clinical trials. The consent form and drug information section have been updated to include updated risk tables based upon the most recent MLN8237 Investigators Brochure. Additional minor edits are also included.

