10.2.2 Evaluable for Response

Eligible patients with measurable or evaluable disease who receive ≥ 5 of the 7 planned doses of MLN8237, ≥ 4 of the 5 planned doses of irinotecan, and ≥ 4 of the 5 planned doses of temozolomide in cycle 1 are evaluable for response. Eligible patients with measurable or evaluable disease who fail to complete one course of therapy because of disease progression are also evaluable for response. Response will be described for all patients entered on study.

All patients who are registered onto the study must be assessed for response to treatment, even if there are major protocol treatment deviations or if they are ineligible or not evaluable. Each patient will be assigned one of the following categories (see Section 11.4):

- a. Complete response
- b. Very good partial response
- c. Partial response
- d. Stable disease
- e. Mixed response
- f. Progressive disease
- g. Early death from malignant disease
- h. Early death from toxicity
- i. Early death because of other cause
- j. In-evaluable (not assessable, insufficient data, patients off therapy early due to toxicity)

k. Never received any of the study drugs, MLN8237, irinotecan, or temozolomide

All eligible patients who receive study therapy will be included in the initial analysis of response. Patients in groups a through c will be classified as responders; patients in groups d through j will be classified as non-responders. In a second analysis, the proportion of responders (patients in groups a through c) will be calculated from the subset of patients who are evaluable for response (as defined above).

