10.4 Statistical Rules for the Phase 2 Portion

The phase II portion at the MTD will enroll patients in two stages. A maximum of 20 patients will contribute response data reflecting patients treated at the recommended dose of the combination of MLN8237, irinotecan, and temozolomide.

	Cumulative Number of Responses	Decision / Action
Stage 1: Enter 14 patients	≤ 0	Terminate the trial because the combination is not sufficiently effective (i.e. ORR < 15%)
	≥ 1	Continue trial (proceed to Stage 2), providing toxicity is acceptable
Stage 2: Enter 6 additional patients (total of 20 patients)		Construct a 95% confidence interval for the objective response rate

Under the hypothesis of a true response rate that is 15% or greater (derived from response rate in COG protocol ANBL0421 with irinotecan and temozolomide), there is a 90% chance that at least 1 of the 14 patients in Stage 1 of the expansion will experience an objective response (hence no responders in 14 patients will lead us to conclude that the true response rate is less than 15%). With 20 patients, the half-width of a two-sided 95% confidence interval will be no more than +/- 0.24 (using the method of Jennison and Turnbull to adjust for the two-stage design). Completion of enrollment to stage 2 is therefore designed to provide a more precise estimate of the response rate of this regimen.

Toxicity Monitoring Plans for the Phase II Portion

For the patients enrolled during the Phase II portion at the MTD, the following rules will be used to monitor toxicity and trigger a formal review of the all the toxicities, with the possibility of reducing the dose (applies to the new patients):

- If 2 patients experience a first course DLT (at least possibly attributed to the study drugs) in the 1st 6 patients
- If 3 patients experience a first course DLT (at least possibly attributed to the study drugs) in the 1st 9 patients
- If 4 patients experience a first course DLT (at least possibly attributed to the study drugs) in the 1st 12 patients
- If 5 patients experience a first course DLT (at least possibly attributed to the study drugs) in the 1st 15 patients
- If 6 patients experience a first course DLT (at least possibly attributed to the study drugs) in the 1st 18 patients
- If 7 patients experience a first course DLT (at least possibly attributed to the study drugs)

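### Section 10.6.2 does not limit the EFS and OS analyses to the MTD, so the written analysis does not estimate Aim 1.5; the general response wording needs aligning with section 10.4

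*Combined protocol and SAP*

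**What the plan says.** The secondary aim (section 1.0, Aim 1.5) is: "To determine the progression free survival rates for patients with relapsed or refractory neuroblastoma treated with MLN8237, irinotecan, and temozolomide at the identified MTD". Primary Aim 1.4, on response, carries the same limit to the MTD.

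The analysis text is broader. Section 10.6.2 says "All eligible patients who begin treatment will be included in the analysis of overall survival, event-free survival (EFS), and best response", and section 10.2.2 says of response "All eligible patients who receive study therapy will be included in the initial analysis of response". A second response analysis follows in 10.2.2, in which "the proportion of responders (patients in groups a through c) will be calculated from the subset of patients who are evaluable for response". None of these sentences names a study portion, a dose level or a formulation. The toxicity section just before, 10.6.1, does ask for tables split by formulation, dose level and course.

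Response also has a specific rule. Section 10.4, on the phase 2 portion at the MTD, says "A maximum of 20 patients will contribute response data reflecting patients treated at the recommended dose" and builds the two-stage 95% interval on them. Section 2.13 adds that "Amendment #6 formally separates the phase I and phase II portions of the study", and the abstract says "In the phase II portion of the study, the primary aim is to determine the objective response rate of this combination". No comparable rule exists for EFS or OS.

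**The concern.** A statistician who follows 10.6.2 as written would put quite different treatments into one EFS curve and one OS curve:

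- tablets at 45, 60 and 80 mg/m²;
- level 1, where growth factor and cephalosporin support were optional, next to levels where they were required;
- the oral solution, whose AUC relative to the capsule is given in section 2.12 as 1.26 (90% CI 1.09-1.47).

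That curve describes the whole trial population. It does not describe the regimen at the MTD, which is what Aim 1.5 asks about. Aim 1.5 is the only secondary aim, and 10.6.2 is the only place where an analysis set for time-to-event outcomes is written down. A stated rule therefore conflicts with the aim it should serve.

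For response, the same general wording sits beside the specific rule in 10.4, and the two are not reconciled.

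**Working it through.** **Inputs.**
- Phase 1: 22 patients (section 10.1). By level: 6 at level 1 (section 2.11), then 6 at 1B, 6 at 2B and 4 evaluable at 3B (section 2.12). Check: 6 + 6 + 6 + 4 = 22.
- Phase 2: 14-20 new patients (10.1), at most 20 (10.4), all on tablets at 2B (4.2.1, 4.3).
- Oral solution cohort: 6-18 patients (10.1), starting at 1B, with -1B or 2B possible (4.3).

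**The plan's own figures (10.4).**
- Chance of at least one response in 14 at a true rate of 15%: 1 - 0.85^14 = 1 - 0.103 = 0.897. The plan states 90%.
- Largest half-width of the Jennison-Turnbull 95% interval with 20 patients: 0.228, at 10/20. The plan states no more than 0.24.

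Both reproduce. The second is stated for 20 patients, which supports reading the response interval as a phase 2 quantity.

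**Size of the literal 10.6.2 set, phase 2 fully enrolled.**
- Lower end: 22 + 20 + 6 = 48.
- Upper end: 22 + 20 + 18 = 60.

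| Subset | n | Share of 48 | Share of 60 |
|---|---|---|---|
| Phase 2 | 20 | 20/48 = 42% | 20/60 = 33% |
| Tablets at 2B, both phases | 20 + 6 = 26 | 26/48 = 54% | 26/60 = 43% |
| Everyone else | 22 to 34 | 22/48 = 46% | 34/60 = 57% |

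**Effect on an EFS estimate.** The documents give no EFS by dose level, so neither the direction nor the size of the shift can be known. At a fixed time, ignoring censoring, the pooled proportion minus the 2B tablet proportion equals (share of everyone else) × (their proportion minus the 2B tablet proportion). Each 10 points of assumed difference between the groups therefore moves the pooled estimate by 0.46 × 10 = 4.6 to 0.57 × 10 = 5.7 points. If the groups do not differ, there is no shift.

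**Does the choice of set change a planned decision on response?** Response counts are not in the documents; the following are assumed.
- Phase 2 alone, 7/20: 35% (95% CI 15.4-59.2%).
- Adding 4 responses among the other 28: 11/48 = 22.9% (12.0-37.3%).

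The estimate moves, and the interval goes from excluding 15% to including it. But 7/20 is the smallest count whose lower limit exceeds 15%, so the example sits at the edge. Intervals wholly on opposite sides of 15% cannot occur: with 7 responders, the lowest possible pooled upper limit is 22.6%, at 7/60. After stage 2 the plan only constructs an interval and has no success rule. The stage 1 rule (stop at 0 of 14) uses phase 2 patients only.

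**The case against.** The best defence is that 10.2.2 and 10.6.2 settle a different question, namely all treated patients against the evaluable subset, and say nothing about merging portions. Where the protocol means to merge portions it says so: section 10.8 states that the final pharmacokinetic analysis draws on phase 1, phase 2 and the oral solution cohort. On this view 10.6.2 applies within each portion, Aim 1.5 supplies the MTD limit for PFS, and 10.4 governs response. In addition, OS appears in no aim, and no test or precision target depends on EFS or OS.

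Much of this stands for response. A reader might infer that the primary response estimate is left open among several populations. The documents do not support that: 10.4, the separation of phases in 2.13, the count of new patients in 10.1 and the abstract together point to the 14-20 phase 2 patients.

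It does not dispose of the EFS and OS point. Application within each portion is a possible reading, but it is not written, and the split by dose level and formulation in 10.6.1 is missing from 10.6.2. Aim 1.5 cannot supply the limit either, because it is the text with which 10.6.2 conflicts. Nor is the phrase "treated with MLN8237, irinotecan, and temozolomide at the identified MTD" enough to define a set. It would admit the six phase 1 patients at 2B, and section 10.5 foresees a separate MTD for the oral solution.

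**Conclusion.** The point holds for EFS and OS. Read literally, 10.6.2 analyses about 48-60 patients, of whom 33-42% are phase 2 and 43-54% took tablets at 2B, and this does not estimate Aim 1.5. The counts assume full phase 2 enrolment, the planned oral cohort sizes, and that all treated patients are eligible. The bias in the EFS estimate cannot be quantified from the documents.

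For response the defect is one of alignment: the general wording in 10.2.2 and 10.6.2 should be made consistent with 10.4. A reader might go further and infer that the choice of set could reverse the trial's conclusion. That is not shown. It rests on assumed response counts and on comparing the final interval with 15%, a comparison the plan does not make after stage 2. The stage 1 rule is unaffected.

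**What to change.** In 10.2.2 and 10.6.2, state that:

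- the primary response estimate uses eligible treated phase 2 patients, with the Jennison-Turnbull interval of 10.4;
- the PFS/EFS estimate for Aim 1.5, and OS, are reported for eligible patients treated with tablets at the MTD (2B). Phase 2 patients are the main set, and any estimate that adds the six phase 1 patients at 2B is labelled supportive;
- the other phase 1 dose levels and the oral solution cohort are reported separately and descriptively, by dose level and formulation, as 10.6.1 does for toxicity;
- any estimate pooled across these groups is exploratory.

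The same edit should say that EFS as defined in 10.6.2 is the measure that answers Aim 1.5, since the aim names progression-free survival and 10.6.2 defines only EFS.

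The cost is a few sentences and some extra table rows; sample size and the 10.4 design figures do not change. The drawback is precision. If interval width scales with 1/√n and event rates are similar, the EFS and OS intervals from 20 patients would be about √(48/20) = 1.55 to √(60/20) = 1.73 times as wide as pooled ones.
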